### Sensitivity Analysis

A sensitivity analysis of the primary endpoint will use the same generalized linear mixed effect model as the principal analysis, but with jump to reference (J2R) to impute missing data in months 1 to 3 using N = 1000 datasets. The imputation model will use the following variables: age, sex, race, prophylactic migraine medication use at randomization, and the number of migraine days per month in the OP. Race may be reduced to fewer levels (e.g., white versus non-white) based on the availability of data.

### Subgroup Analyses

Subgroup analyses of the primary endpoint will use the same generalized linear mixed effect model specified for the principal analysis of the primary endpoint, except without prophylactic migraine medication use at randomization. The following model estimates will be reported for each subgroup level of all efficacy subgroups of interest specified in Section 6.1.3.1, except prophylactic migraine medication use at randomization:

- LSM change from OP, SE, and 95% CI by month for each treatment group
  - Difference in LSM changes from OP between treatment groups (rimegepant – placebo), SE, 95% CI, and p-value by month
  - Overall LSM change from OP, SE, and 95% CI for each treatment group
  - Difference in overall LSM changes from OP between treatment groups (rimegepant – placebo), SE, 95% CI, and p-value.
-

### 6.3.1.2 *Reduction in Migraine Days per Month in the OLE Phase*

The number of migraine days per month in the OLE phase will be examined relative to the number of migraine days per month in the OP for evaluable OL rimegepant mITT subjects, i.e., mITT subjects with ≥ 14 days of eDiary efficacy data (not necessarily consecutive) in both the OP analysis period and ≥ 1 month (i.e., 4-week interval) in the on-OL rimegepant efficacy analysis period. Results will support an exploratory objective.

Months in the OLE phase will be defined as:

- Month 1 (> 12 to ≤ 16 weeks; study days 85 to 112)
- Month 2 (> 16 to ≤ 20 weeks; study days 113 to 140)
- Month 3 (> 20 to ≤ 24 weeks; study days 141 to 168)
- Month 4 (> 24 to ≤ 28 weeks; study days 169 to 196)
- Month 5 (> 28 to ≤ 32 weeks; study days 197 to 224)
- Month 6 (> 32 to ≤ 36 weeks; study days 225 to 252)
- Month 7 (> 36 to ≤ 40 weeks; study days 253 to 280)
- Month 8 (> 40 to ≤ 44 weeks; study days 281 to 308)
- Month 9 (> 44 to ≤ 48 weeks; study days 309 to 336)
- Month 10 (> 48 to ≤ 52 weeks; study days 337 to 364)
- Month 11 (> 52 to ≤ 56 weeks; study days 365 to 392)
- Month 12 (> 56 to ≤ 60 weeks; study days 393 to 420)
- Month 13 (> 60 to ≤ 64 weeks; study days 421 to 448).

Analyses will be based on eDiary efficacy dates in the OP analysis period and on-OL rimegepant efficacy analysis period.

The number of migraine days per month will be prorated to 28 days, and derived as follows:

- OP: See Section 6.3.1.1.
- Month (i.e., 4-week interval) in the on-OL rimegepant efficacy analysis period:  $28 \times (\text{total number of migraine days in the month}) / (\text{total number of efficacy data days in the month})$ .  
Subjects must have ≥ 14 days of efficacy data (not necessarily consecutive) in the specified month to be evaluable.

- Overall OL rimegepant mean:  $28 \times (\text{total number of migraine days through Month 13 in the on-OL rimegepant efficacy analysis period}) / (\text{total number of efficacy data days through Month 13 in the on-OL rimegepant efficacy analysis period})$ .

### Missing Efficacy Data

Missing efficacy data in the OP and OLE phases will be assessed using the number and percentage of OL rimegepant mITT subjects by treatment group and overall in the following categories:

- Evaluable
- Not evaluable, i.e., < 14 days of efficacy data in the OP and all 13 months (i.e., all 13 4-week intervals) in the OLE phase
  - < 14 days of efficacy data in the OP
  - < 14 days of efficacy data in any of the following months in the OLE phase:
    - Months 1 to 3: > 12 to  $\leq$  24 weeks
    - Months 4 to 6: > 24 to  $\leq$  36 weeks
    - Months 7 to 9: > 36 to  $\leq$  48 weeks
    - Months 10 to 13: > 48 to  $\leq$  64 weeks

### Descriptive Analyses

Analyses are based on evaluable OL rimegepant mITT subjects.

Values and changes (both absolute and percent) from the OP in the number of migraine days per month in the OLE phase will be summarized descriptively as continuous parameters (including 2-sided normal 95% CIs for mean change) by treatment group (including overall) and severity (total; moderate or severe) in each month of the OLE phase and overall OL mean. Results will support the exploratory objective about OLE phase efficacy.

A scatter plot by treatment group will display the change in the number of total migraine days per month in the OL overall mean (y-axis) versus number of migraine days per month in the OP (x-axis). Another scatter plot by treatment group will display the percent change in the number of total migraine days per month in the OL overall mean (y-axis) versus number of migraine days per month in the OP (x-axis). Plots will include a horizontal reference line at 0.

A longitudinal plot will display the mean change from OP in the number of total migraine days per month (y-axis) versus month of the OLE phase (x-axis). Another longitudinal plot will display the mean change from OP in the number of moderate or severe migraine days per month (y-axis) versus month of the OLE phase (x-axis). Error bars will denote 95% CIs.

In the percent change analyses, subjects must also have  $\geq 1$  migraine day (i.e., absolute not prorated to 28 days) of appropriate severity in the OP analysis period to be included.

---

## 6.3.2 Secondary Efficacy Endpoints

### 6.3.2.1 Percentages of Subjects with Reduction in Migraine Days per Month

Analyses will be based on evaluable mITT subjects and evaluable OL rimegepant mITT subjects.

In analyses by months, subjects must (1) achieve the reduction criterion from OP in the number of migraine days in the specified month, (2) be evaluable (i.e., have  $\geq 14$  days of efficacy data [not necessarily consecutive]) in the specified month, and (3) have  $\geq 1$  migraine day (absolute not prorated to 28 days) of appropriate migraine severity in the OP analysis period to be classified as responders in the specified month. Otherwise, subjects will be classified as failures in the specified month.

In analyses of the overall DBT or OLE mean, subjects must (1) achieve the reduction criterion from OP in the number of migraine days in the overall mean, and (2) have  $\geq 1$  migraine day (absolute not prorated to 28 days) of appropriate migraine severity in the OP analysis period to be classified as responders. Otherwise, subjects will be classified as failures.

#### Percentages of Subjects With Reduction in Migraine Days per Month in the DBT Phase

Analyses will be based on evaluable mITT subjects with eDiary efficacy dates in the OP and on-DBT efficacy analysis periods (see Section 6.3.1.1).

#### Descriptive Analyses

The number and percentage of evaluable mITT subjects with reductions from the OP in the number of migraine days per month in the DBT phase will be presented by treatment group and severity (total; moderate or severe) in each month of the DBT phase and overall DBT mean (see Section 6.3.1.1 for months). Reduction from OP categories will be:  $\geq 1$ ,  $\geq 2$ ,  $\geq 3$ ,  $\geq 4$ ,  $\geq 5$ ,  $\leq 0$ ;  $> 0$  to  $\leq 2$ ;  $> 2$  to  $\leq 4$ ;  $> 4$  to  $\leq 6$ ;  $> 6$  to  $\leq 8$ ;  $> 8$  to  $\leq 10$ ;  $> 10$  to  $\leq 12$ ;  $> 12$  to  $\leq 14$ ;  $> 14$ ;  $\geq 20\%$ ,  $\geq 25\%$ ,  $\geq 30\%$ ,  $\geq 35\%$ ,  $\geq 40\%$ ,  $\geq 45\%$ ,  $\geq 50\%$ ,  $\geq 75\%$ , and  $\geq 100\%$ . Analyses by month will be presented using the following 2 methods:

- Non-Evaluable = Failure: Analyses will be based on all evaluable mITT subjects in all months. An additional reduction category “Not evaluable” will be included.
- Non-Evaluable = Missing: Evaluable mITT subjects with  $\geq 1$  migraine day of appropriate migraine severity in the OP analysis period and  $< 14$  days of efficacy data in the specified month will be excluded from analyses of the specified month.

The number and percentages of evaluable mITT subjects with reduction outcomes will be presented by treatment group in each month of the DBT phase and overall DBT mean for each migraine severity (total; moderate or severe) and select percentage reduction ( $\geq 50\%$ ,  $\geq 75\%$ , and  $\geq 100\%$ ). Outcomes categories at each month will be defined as follows:

- Responder, i.e., subjects with  $\geq 14$  days of efficacy data in the specified month,  $\geq X\%$  reduction in the specified month, and  $\geq 1$  migraine day of appropriate migraine severity in the OP analysis period.

- Failure
  - No migraine days of appropriate migraine severity in the OP.
  - Evaluable but  $< X\%$  reduction in the month, i.e., subjects with  $\geq 14$  days of efficacy data and  $< X\%$  reduction in the specified month.
  - $\geq X\%$  reduction but not evaluable in the month, i.e., subjects with  $\geq X\%$  reduction and  $\geq 1$  to  $< 14$  days of efficacy data in the specified month.
  - $< X\%$  reduction but not evaluable in the month, i.e., subjects with  $< X\%$  reduction and  $\geq 1$  to  $< 14$  days of efficacy data in the specified month.
  - No days of efficacy data in the month.

Outcomes categories for the overall DBT mean will be defined as follows:

- Responder, i.e., subjects with  $\geq X\%$  reduction in the overall DBT mean and  $\geq 1$  migraine day of appropriate migraine severity in the OP analysis period.
- Failure
  - No migraine days of appropriate migraine severity in the OP.
  - $< X\%$  reduction, i.e., subjects with  $< X\%$  reduction in the overall DBT mean.

In the above description,  $X = 50, 75,$  and  $100$ . Failure subcategories are mutually exclusive, because subjects who meet more than 1 failure criterion will be classified according to the first failure criterion met in the hierarchy above.

The following histograms will be produced by treatment group for evaluable mITT subjects:

- Percentage of subjects in categories of reduction from OP in the number of total migraine days per month in the last month of the DBT phase (y-axis) versus reduction category (x-axis). This is based on evaluable mITT subjects in Month 3.
- Percentage of subjects in categories of reduction from OP in the number of total migraine days per month in the overall DBT mean (y-axis) versus reduction category (x-axis).

Reduction categories are displayed in descending order:  $> 14$ ;  $> 12$  to  $\leq 14$ ;  $> 10$  to  $\leq 12$ ;  $> 8$  to  $\leq 10$ ;  $> 6$  to  $\leq 8$ ;  $> 4$  to  $\leq 6$ ;  $> 2$  to  $\leq 4$ ;  $> 0$  to  $\leq 2$ ; increase or no reduction in migraine days/month (i.e.,  $\leq 0$ ). Histograms will include a vertical reference line between the last 2 categories. Histograms were included as adhoc analyses in the CSR.

### Treatment Group Comparisons

For each migraine severity (total; moderate or severe) and select percentage reductions ( $\geq 50\%$ ,  $\geq 75\%$ , and  $\geq 100\%$ ), the percentages of evaluable mITT subjects with reductions will be compared between treatment groups using Cochran-Mantel-Haenszel (CMH) tests stratified by prophylactic migraine medication use at randomization (yes, no). Response rates will be based on responder outcomes described previously. The following statistics will be presented for each month of the DBT phase and overall DBT mean by migraine severity:

- Response rate (“n/N”), risk (i.e., percentage), ASE, and 95% normal CI by randomization stratum for each treatment group
- Overall response rate (“n/N”), stratified risk, ASE, and 95% normal CI for each treatment group
- Difference in risks between treatment groups (rimegepant – placebo), ASE, 95% CI, and p-value by randomization stratum
- Difference in overall stratified risks between treatment groups (rimegepant – placebo), ASE, 95% CI, and p-value.

Results for  $\geq 50\%$  reduction of moderate or severe migraine severity in the last month (i.e., month 3) will support the first secondary objective. All other results will support exploratory objectives about percentage reductions.

These endpoints will also be compared between treatment groups using unstratified CMH tests by migraine severity (total; moderate or severe) for each subgroup level of all efficacy subgroups of interest specified in Section 6.1.3.1 except prophylactic migraine medication use. For each migraine severity and subgroup level, the following statistics will be presented for each month in the DBT phase and overall DBT mean:

- Response rate (“n/N”), risk (i.e., percentage), ASE, and 95% normal CI by treatment group
- Difference in risks between treatment groups (rimegepant – placebo), ASE, 95% CI, and p-value.

Longitudinal plots will display the percentage of subjects with reduction (i.e., overall stratified risks on y-axis) versus month of the DBT phase (x-axis) for each select percentage reduction ( $\geq 50\%$ ,  $\geq 75\%$ , and  $\geq 100\%$ ) and migraine severity (total; moderate or severe). Error bars will denote 95% CIs.

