### **1.2.3 Exploratory Objectives**

- To compare the efficacy of rimegepant to placebo on the reduction from baseline in the mean number of migraine days per month by severity (total; moderate or severe) in each month and the entire course of the DBT phase.
  - To compare the efficacy of rimegepant to placebo on the proportion of subjects who have at least a 50% reduction from baseline in the mean number of migraine days per month by severity (total; moderate or severe) in each month and the entire course of the DBT phase.
  - To evaluate the reduction in the number of migraine days per month by severity (total; moderate or severe) in each month and the entire course of the OLE phase.
  - To compare the efficacy of rimegepant to placebo as a preventive treatment for menstrually-related migraine (MRM), as measured by the reduction from baseline in the mean number of MRM days per month in each month and the entire course of the DBT phase.
  - To compare the efficacy of rimegepant to placebo on the proportion of subjects who have at least a 75% reduction from baseline in the mean number of migraine days per month by severity (total; moderate or severe) in each month and the entire course of the DBT phase.
  - To compare the efficacy of rimegepant to placebo on the proportion of subjects who have a 100% reduction from baseline in the mean number of migraine days per month by severity (total; moderate or severe) in each month and the entire course of the DBT phase.
  - To evaluate the frequency of elevated liver function tests (LFT: AST, ALT, or TBL) in subjects treated with rimegepant.
  - To evaluate the frequency of subjects with ALT or AST elevations  $> 3x$  ULN in temporal association with nausea, vomiting, anorexia, abdominal pain, or fatigue in subjects treated with rimegepant.
  - To evaluate the effect of rimegepant treatment on the MSQoL v2.1 domain scores.
  - To evaluate the effect of rimegepant treatment on the Migraine Preference of Medication (PoM).
  - To evaluate the effect of rimegepant treatment on the Satisfaction with Medication (SM).
  - To evaluate the effect of rimegepant treatment on the MIDAS scores.
-

- To evaluate the effect of rimegepant treatment on the Clinical Global Impression of Change (CGI-c) scale.
- To compare the efficacy of rimegepant to placebo on the reduction from baseline in the mean number of migraine days per week by severity (total; moderate or severe) in the first week of the DBT phase.

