#### 6.1.3.1 Efficacy Subgroups for Evaluable mITT Subjects

For evaluable mITT subjects, the following efficacy subgroups are of interest:

- Age:  $< 40$ ,  $\geq 40$ ,  $< 65$ ,  $\geq 65$
- Sex: female, male
- Race: White, Black or African American, Other Including Asian, Asian
- Ethnicity: Hispanic or Latino, Not Hispanic or Latino
- Baseline body mass index (BMI; kg/m^2):  $< 25$ ,  $\geq 25$  to  $< 30$ ,  $\geq 30$
- Historical number of moderate or severe migraine attacks per month:  $< 6$ ,  $\geq 6$ ,  $< 8$ ,  $\geq 8$ ,  $< 12$ ,  $\geq 12$ ,  $< 15$ ,  $\geq 15$
- Historical primary migraine type: migraine with aura, migraine without aura
- Historical chronic migraine: yes, no
- Prophylactic migraine medication use at randomization (i.e., IWRS randomization strata): yes, no
- Total migraine days per month in the OP:  $< 14$ ,  $\geq 14$ .

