## **6.3 Efficacy**

Efficacy endpoints will be assessed by as-randomized treatment group.

Randomization is stratified by prophylactic migraine medication use at randomization (i.e., IWRS randomization stratum; yes or no). Hence, treatment group comparisons of continuous efficacy endpoints will be *adjusted* by prophylactic migraine medication use at randomization, whereas treatment group comparisons of binary efficacy endpoints will be *stratified* by prophylactic migraine medication use at randomization (except in subgroup analyses). If there are sparse data within a stratum, then results may be presented unstratified.

In treatment comparisons of binary efficacy endpoints, CIs will be based on a normal approximation to the binomial distribution using asymptotic standard error (ASE). Otherwise, CIs for continuous efficacy endpoints will be based on the normal distribution. All CIs will be 2-sided.

Select efficacy listings will display efficacy analysis period (i.e., OP, on-DBT, on-OL rimegepant, and follow-up). See Sections 7.4 and 7.5 for the definition of efficacy analysis periods and study days.

The following general by-subject efficacy listings will be provided:

- Subjects excluded from the efficacy analysis for randomized subjects not in the evaluable mITT population sample, including the reason for exclusion (see Section 3).
- Primary and secondary efficacy endpoints for randomized subjects, including the reason for exclusion from the evaluable mITT population sample (see Sections 6.3.1.1 and 6.3.2)
- Exploratory endpoints for mITT subjects (see Section 6.3.3).

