### 6.6.3 CGI-c Scale

The CGI-c is an observer-rated 7-point scale that measures patient total improvement relative to the investigator's past experience with other patients with the same diagnosis, with or without collateral information. The 7 improvement categories are: very much improved, much improved, minimally improved, no change, minimally worse, much worse, and very much worse.

The number and percentage of treated subjects in each category (including combined categories) will be presented by treatment group and overall at the following time points: Week 12 and last visit of the DBT OR analysis period; and Weeks 24, 64, and last visit of the OL rimegepant OR analysis period. Percentages for categories will be based on subjects with non-missing data at each visit along with 2-sided Agresti-Coull 95% CIs for each percentage. Refer to the BHV3000 Core SAP for combined categories.

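### Normal-approximation intervals for responder rates collapse or run too narrow in sparse exploratory subgroup and stratum cells, most visibly at the 100% reduction threshold

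*SAP*

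**What the plan says.** SAP 6.3 (Efficacy) sets one rule for treatment comparisons of binary efficacy endpoints: "CIs will be based on a normal approximation to the binomial distribution using asymptotic standard error (ASE". It adds "All CIs will be 2-sided".

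SAP 6.3.2.1 (DBT phase, Treatment Group Comparisons) applies the rule to reductions of at least 50%, 75% and 100%, for two severities, in each of three months and in the overall double-blind mean. Results are given by randomization stratum, overall, and "for each subgroup level of all efficacy subgroups of interest specified in Section 6.1.3.1 except prophylactic migraine medication use". Each subgroup level gets "risk (i.e., percentage), ASE, and 95% normal CI by treatment group" and "Difference in risks between treatment groups (rimegepant – placebo), ASE, 95% CI, and p-value". The 100% threshold is an exploratory objective in SAP 1.2.3: "proportion of subjects who have a 100% reduction from baseline in the mean number of migraine days per month by severity".

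Some levels in SAP 6.1.3.1 may be small, for example "Race: White, Black or African American, Other Including Asian, Asian", or age 65 and over. Two provisions touch on sparse data. SAP 6.1.3 permits levels to be redefined or merged depending on available data, and SAP 6.3 permits an unstratified display. Both are optional, neither has a threshold, and neither changes the interval formula.

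Elsewhere the documents choose other intervals for proportions. SAP 6.6.3 to 6.6.5 report CGI-c, PoM and SM percentages "along with 2-sided Agresti-Coull 95% CIs for each percentage", and Protocol 9.5 asks for exact intervals for the rare combined liver-test elevations.

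**The concern.** The normal-approximation (Wald) interval takes its width from the observed proportion. When that proportion is zero the estimated standard error is zero, so the table shows complete certainty in a cell that carries little information. With one or two responders the interval has some width, but often too little.

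The design makes such cells foreseeable. A 100% responder must have no migraine days of the relevant severity in the period, whereas entry requires at least 6 migraine days in the Observation Period (Protocol 5.2). In the monthly analyses, subjects with fewer than 14 diary days count as failures (SAP 6.3.2.1). Eligibility also narrows some levels: BMI of 30 and over stops below 33 (Protocol 5.3), and 15 or more historical attacks stops at 18 (Protocol 5.2).

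Subgroup tables are read to judge whether the effect is consistent. Intervals that are falsely tight can make a sparse level look settled when it is only uninformative.

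**Working it through.** **The plan's own figure.** SAP 5 expects 370 evaluable subjects per arm, a 1-day difference and an SD of 3.75, with roughly 95% power. The standard error is 3.75 × √(2/370) = 0.276. The ratio is 1/0.276 = 3.63, and Φ(3.63 − 1.96) gives 95.2%. The figure reproduces, and 370 per arm is used below for full-arm results. The documents state no responder rate, subgroup size or coverage.

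**Number of cells.** Levels in SAP 6.1.3.1 without prophylactic medication use: age 4 + sex 2 + race 4 + ethnicity 2 + BMI 3 + historical attacks 8 + migraine type 2 + chronic migraine 2 + Observation Period migraine days 2 = 29. They overlap (for example age under 40 and under 65). For the 100% threshold: 29 × 2 severities × 4 periods = 232 risk-difference intervals and 232 × 2 arms = 464 single-arm intervals. This is how many intervals use the method, not how many would fail.

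**Zero responders.** The single-arm interval is p ± 1.96 × √(p(1 − p)/n). At p = 0 it is 0% to 0% for any n. With 0/20, the Agresti-Coull upper limit is 19.0% and Wilson's is 16.1%.

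**Differences.** The variance is p1(1 − p1)/n1 + p2(1 − p2)/n2. With both arms at 0 the interval is 0 to 0. With one arm at 0, that arm's term disappears. Illustration, 2/20 versus 0/20:

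- Wald: 0.10 ± 1.96 × √(0.1 × 0.9/20 + 0) = 0.10 ± 0.131, or −3.1% to 23.1%.
- Newcombe, from Wilson limits of 2.8% to 30.1% and 0% to 16.1%: −7.7% to 30.1%.

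**Coverage under assumed sizes and rates**, by summing exact binomial probabilities over all outcomes.

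Single arm, nominal 95%:

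| n | true rate | chance of 0 responders | Wald | Agresti-Coull | Wilson |
|---|---|---|---|---|---|
| 20 | 5% | 35.8% | 63.9% | 98.4% | 92.5% |
| 60 | 5% | 4.6% | 80.6% | 97.0% | 97.0% |
| 60 | 2% | 29.8% | 70.1% | 96.8% | 96.8% |
| 370 | 5% | below 0.1% | 94.8% | 94.5% | 94.5% |

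Hand check at n = 60, 5%. Zero responders has probability 0.95^60 = 4.6%. One responder has probability 60 × 0.05 × 0.95^59 = 14.6%, and its upper limit is 1.67% + 3.24% = 4.91%, just below 5%. These two outcomes account for 19.2 of the 19.4 points missed.

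Risk difference, 5% versus 2%:

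| n per arm | chance both arms at 0 | Wald | Newcombe |
|---|---|---|---|
| 20 | 23.9% | 75.6% | 99.8% |
| 40 | 5.7% | 86.3% | 98.7% |
| 60 | 1.4% | 93.9% | 98.3% |
| 100 | 0.1% | 93.6% | 96.8% |
| 370 | below 0.1% | 94.6% | 95.6% |

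At 10% versus 5%, Wald covers 85.8% at 20 per arm and 93.9% at 40. For rates typical of a 50% responder endpoint (50% versus 40% assumed), it covers 95.0% at 370 per arm.

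**The case against.** The strongest reply is that nothing decisive rests on these intervals. SAP 6.3.2.1 assigns every responder result except the 50% moderate-or-severe endpoint in month 3 to exploratory objectives, and SAP 6.1.2 makes exploratory p-values descriptive. The tables print n/N beside each interval, so 0/20 is visible. The treatment contrast is the more important output, and its coverage is already about 94% at 60 per arm, so the shortfall there is confined to quite small levels. Levels may be merged, and merging adds responders. All of this stands, and it keeps the point minor. Merging is only partial protection, because it is discretionary, and a single arm of 60 at a 2% rate still has only 70% coverage.

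A reader might infer that the longitudinal plots would show zero-width error bars. The documents do not support that. The plots show overall stratified risks in full arms of about 370, and even at an assumed 2% rate an arm with no responders has probability 0.98^370, about 0.06%.

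A reader might also see a contradiction with the Agresti-Coull intervals in SAP 6.6. Those apply to descriptive, as-treated percentages, so the difference in method is not an inconsistency. It shows only that a better interval is already in use within the same plan.

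**Conclusion.** The concern holds for the exploratory subgroup-level and by-stratum response tables. The zero-width interval for an arm without responders follows directly from the formula and needs no assumption. The coverage figures do need assumptions: true rates of 2% to 10% and 20 to 100 subjects per arm. Within that range single-arm coverage can fall well below 95%, while difference coverage falls materially short only at about 40 per arm or fewer.

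It would go too far to say that nominal coverage fails in all 29 levels. Subgroup sizes and 100% response rates are not given, and many levels may be large enough. A zero-width difference interval requires both arms to be at 0% (or both at 100%, or one at each). With one arm at 0 and the other in between, the interval is too narrow but does not collapse. The first hierarchical secondary endpoint is essentially unaffected, because the method is adequate at about 370 per arm and its p-value comes from the CMH test. Severity is minor.

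**What to change.** In SAP 6.3 and 6.3.2.1, limit the change to the subgroup-level and by-stratum response tables. Use Agresti-Coull (as in SAP 6.6.3 to 6.6.5) or Wilson intervals for each arm's rate, and Newcombe or Miettinen-Nurminen intervals for the unstratified risk difference.

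Leave unchanged the point estimates, the CMH tests, the overall stratified estimates and the interval for the hierarchical secondary endpoint. The current method is adequate for the full arms, and a single-binomial Wilson or Agresti-Coull interval does not apply directly to a stratified risk.

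The cost is one sentence and a standard software option. Intervals in sparse cells become wider and mostly conservative: Newcombe covers 98% to 99.8% in the 5% versus 2% cells at 20 to 60 per arm. Wilson can still fall slightly short, at 92.5% with 20 subjects and a 5% rate. The SAP's revision history places version 10.0 after the final database lock, and the double-blind comparisons belong to the Week 12 unblinded analysis (SAP 4), so the change should be labelled as made after lock.
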